6.0 Significance

This will be the first study examining the clinical efficacy of combined FMT and fidaxomicin in the treatment of severe or fulminant CDI refractory to medical therapy. Longitudinal clinical samples collected during this study will undergo detailed analysis to gain better understanding of the complex interaction between microbiome and human host in this context. Results from this study have the potential to stimulate further studies aimed at elucidating mechanisms of action of FMT in order to develop rational microbiome based therapy. The knowledge gained during this trial will help us optimize treatment algorithm for patients suffering from treatment refractory CDI, and ultimately improve patient experiences and outcomes while simultaneously decrease health care costs.

Figure 1. Provincial rates of health care associated CDI and attributable mortality to CDI by zone between 2014 and 2016. Alberta Health Services Quality Performance Report 2015-2016. Hospital-acquired Clostridium difficile infections. <http://www.albertahealthservices.ca/assets/about/publications/ahs-pub-pr-2015-16-q2-detail-hospital-acquired-infections.pdf>

The provincial rate of HA-CDI is 3.4 cases per 10,000 patient-days.

[figure not shown]
[figure not shown]

Figure 2.0- Pilot data:

Over the past year, we have successfully treated 6 patients with fulminant CDI with serial FMT plus vancomycin at the University of Alberta. These patients had avoided colectomy as a result. Below are endoscopic images of before (image on the left, showing severe pseudomembranous colitis) and after serial FMT treatment (image on the right, showing normal colon).

[figure not shown]

Figure 3.0
Sequential fecal microbiota transplant protocol proposed.

[figure not shown]
[figure not shown]

Figure 4.0

Proposed sampling for each patient given the protocol seen in Figure 3.0

Appendix A: Universal stool donor testing/screening SOP

Universal stool donors will provide the raw material for FMT. They are screened at baseline and then every 2 months at a minimum for the duration of the trial. They underwent initial detailed history and physical exam, and had been screened with a donor questionnaire, which did not identify any high risk behaviors. They tested negative for all the following potential infections as listed below. They have provided stools for over 300 patients since 2012, and none of the recipients have developed any known infectious complications. All donors are personally known to the investigators. It is simply not practical or cost effective to keep testing them each and every time when there is a scheduled FMT. Since there is no consensus on the mandatory required tests for stool donor, we have chosen the recommendations published by Khoruts et al in the American Journal of Gastroenterology in 2012 as well as the FMT Safety Notice from Health Canada dated July 16, 2019 pertains to MDRO testing, while Mar 25, 2020 pertains to COVID-19

These universal donors have been in the same positions for years are unlikely to move away or stop donating. We have not encountered a situation when a universal donor could not donate on a day when HBT was scheduled to treat patients with recurrent Clostridium difficile infections since Oct 2012. In the unlikely event that he or she can no longer donate, a second donor will be assigned to a particular patient.

We will hold donor FMT materials in quarantine until a donor has passed 2 consecutive screening tests.

On initial history, the donors must fulfill the following inclusion and exclusion criteria:

Donor inclusion criteria:

1. Able to provide and sign informed consent (Appendix D).
2. Able to complete and sign the stool donor questionnaire (Appendix C).
3. Able to adhere to fecal transplantation stool collection standard operating procedure (appendix B).

Donor exclusion criteria:

1. History of any type of active cancer or autoimmune disease (eg multiple sclerosis, connective tissue disease), metabolic syndrome, chronic pain syndrome, and atopic diseases.
2. History of risk factors for acquisition of HIV, syphilis, Hepatitis B, Hepatitis C, prion or any neurological disease as determined by the donor questionnaire (Appendix 2).
3. Gastrointestinal comorbidities, e.g., inflammatory bowel disease, irritable bowel syndrome, chronic constipation or diarrhea, gastrointestinal malignancy or known polyposis.
4. Tattoo or body piercing within 6 months of stool donation.
5. Incarceration or history of incarceration.
6. Receipt of blood transfusion from a country other than Canada in preceding 6 months.
7. Antibiotic use, systemic immunosuppressive or biological agents, systemic antineoplastic agents and exogenous glucocorticoids in the preceding 3 months prior to stool donation.
8. Receipt of any type of live vaccine within 3 months prior to stool donation.

9. Ingestion of nut or shell fish 3 days preceding donation if the recipient has known allergies to these food.
10. Any current or previous medical or psychosocial condition or behaviors which in the opinion of the investigator may pose risk to the recipients or the donor.
11. Travel to areas of the world where diarrheal illnesses or BSE/TSE are endemic (within 6 months of stool donation).
12. High risk of multi-drug resistant organisms, including healthcare workers, recent hospitalization and medical tourism.
13. Travel history outside of Canada within 14 days of screening
14. Exposure to individuals diagnosed with or suspected to have COVID-19 within 14 days of screening
15. History of a fever, cough, sore throat or any other signs of respiratory or other infectious illness in the past 14 days
16. Diagnosis of COVID-19 within the past 3 months

Initial blood work and stool testing, which will be repeated at a minimum of every 2 months.. However, to minimize COVID-19 transmission risk, the quarantine period is at least 5 weeks as per Health Canada directions.

Blood:

- CBC, electrolytes, creatinine, AST, ALT and ALP
- Human Immunodeficiency virus (HIV) 1/2
- hepatitis A IgM Ab
- hepatitis B: HBVsAg, HBVsAb, HBVc Ab (IgM and IgG)
- hepatitis C antibody
- RPR (syphilis)
- human T- lymphotrophic virus (HTLV) I/II

Nasal Swab:

- MRSA

Stool:

- enteric pathogens: *Salmonella*, *Shigella*, *E.coli* O157 H7, *Yersinia*, *Campylobacter* (see Appendices 3-8 for lab SOP)
- *C. difficile* toxin by EIA
- ova and parasites
- VRE
- CRE
- ESBL

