Appendix B: Stool collection instruction for donors (to be filled out with each stool collection)

Stool collection for human biotherapy/ fecal microbiota transplantation

1. Do not take any medications (laxatives, anti-diarrheal drugs, mineral oil, bismuth, magnesium, or kaolin) for at least 3 days prior to and during the specimen collection. If you have been taking antibiotics in the last 90 days, you should not be collecting stool.
2. Make sure you have not had fever, vomiting, diarrhea or other symptoms of infection within the last 30 days. **Inform the investigator if you have any of these symptoms, as you should not donate stool. Please hand in this form with your stool collection with each donation.**

Day of FMT Procedure/donor Checklist		
Donor Name:	Yes	No
Do you feel well and healthy today?		
Have you had any fever, vomiting, diarrhea, cough, sore throat or other symptoms of infection within the last 30 days?		
If yes, specify:		
Antibiotics within past 90 days?		
Any medications (laxatives, anti-diarrheal drugs, mineral oil, bismuth, or magnesium, kaolin) in the past 3 days		
Since your last donation have you started working as a healthcare worker or worked in a long term care facility?		
Since your last donation have you been hospitalized or been treated in a long term care facility?		
Since your last donation, have you had medical treatment requiring frequent, regular attendance at outpatient medical or surgical clinics? If yes, please list dates and reason:		

Since your last donation, have you engaged in medical tourism i.e. travelled outside Canada for medical treatment?			
Since your last donation, have you had contact with anyone who has been diagnosed or suspected to have COVID-19?			
Since your last donation, have you travelled outside of Canada?			
Since your last donation, have you been diagnosed with COVID-19?			

3. Collect the specimen into the commode specimen collection system provided (Fisher 07544208) at home. This system fits under the toilette seat in center of rear of bowl. Do not mix with urine, paper or water. Once stool has been collected, snap on the lid provided to seal the container. Make sure you collect at least 100 g of stool, which is about the size of 4 Timbits donuts.
4. Place the container in the plastic bag supplied by the designate. Seal the bag tightly.
5. Mark date and time of collection and your initials on the lid.
6. Wash hands with soap and water when finished.

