20. Had a blood transfusion?		

21. Had a transplant such as organ, tissue or bone marrow?				
22. Had a graft such as bone or skin?				
23. Come into contact with someone else's blood?				
24. Had an accidental needle-stick?				
25. Had sexual contact with anyone who has HIV/AIDS or has had a positive test for the HIV/AIDS virus?				
26. Had sexual contact with a prostitute or anyone else who takes money or drugs or other payment for sex?				
27. Had sexual contact with anyone who has ever used needles to take drugs or steroids, or anything not prescribed by their doctor?				
28. Had sexual contact with anyone who has hemophilia or has used clotting factor concentrates?				
29. Female donors: Had sexual contact with a male who has ever had sexual contact with another male? (Males: check "I am male")			 I am male	
30. Had sexual contact with a person who has hepatitis?				
31. Had a tattoo?				
32. Had ear or body piercing?				
33. Had or been treated for syphilis, gonorrhea or Chlamydia?				
34. Been in juvenile detention, lockup, jail, or prison for more than 72 hours?				
In the past three years have you				
35. Been outside the United States or Canada? If yes, list the places(s)			 I am female	
From 1980 to the present, have you				
36. Receive a blood transfusion in the United Kingdom or France? (Review list of countries in UK.)				
From 1977 to the present, have you				
37. Received money, drugs, or other payment for sex?				

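### The per-donation donor checklist omits exclusions that Appendix A times to donation (tattoo or piercing, non-antibiotic drugs, live vaccine, nut or shellfish), and no repeat of the fuller questionnaire is stated

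*Protocol*

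**What the plan says.** Appendix A lists the donor exclusions. Several are counted back from the donation:

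- Exclusion 4: "Tattoo or body piercing within 6 months of stool donation".
- Exclusion 7: "Antibiotic use, systemic immunosuppressive or biological agents, systemic antineoplastic agents and exogenous glucocorticoids in the preceding 3 months prior to stool donation".
- Exclusion 8: "Receipt of any type of live vaccine within 3 months prior to stool donation".
- Exclusion 9: nuts or shellfish eaten in the 3 days before donation, when the recipient is known to be allergic.

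Exclusion 5 has no time limit: "Incarceration or history of incarceration".

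Three instruments bear on these exclusions. The Appendix B checklist is marked "to be filled out with each stool collection". The Appendix C questionnaire appears in Appendix A in the past tense: "They underwent initial detailed history and physical exam, and had been screened with a donor questionnaire". Section 3.4 and Appendix A also promise rescreening every 2 months, and Appendix A names the laboratory tests on blood and stool as what is repeated. Material stays in quarantine until the donor has passed two screening tests in a row, and for at least 5 weeks because of COVID-19.

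On incarceration, Appendix C item 34, in the block on the past 12 months, asks: "Been in juvenile detention, lockup, jail, or prison for more than 72 hours".

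**The concern.** An exclusion counted back from each donation can be applied only if someone asks about it at or near each donation. An established donor may take a course of steroids or receive a live vaccine between two collections. If the form handed in with the stool does not ask, the donor can answer every row truthfully and clear it.

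Appendix B is plainly meant to bring the donor's history up to date. Seven of its rows ask what has happened since the previous donation: healthcare work, hospital or long-term care, outpatient care, medical tourism, COVID-19 contact, travel and COVID-19 diagnosis. The omitted exclusions are of the same kind.

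What is at stake is recipient safety. The recipients are severely ill, and proven infection related to FMT is one of the listed serious adverse events. Section 3.4 says that the other sites use an identical donor screening protocol, so a gap in the forms would be shared.

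**Working it through.** No sample size, error rate or event count is involved, so the check is a line-by-line comparison. Exclusions 4, 7, 8, 9 and 11 are the ones worded relative to donation; exclusion 5 is added for the separate mismatch.

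| Exclusion (Appendix A) | Window | Appendix B row | Appendix C item | Addressed by repeat laboratory tests and quarantine |
|---|---|---|---|---|
| 4, tattoo or piercing | 6 months | none | 31 and 32, past 12 months | partly (HIV, hepatitis B and C, syphilis, HTLV) |
| 7, antibiotics | 3 months | yes, 90 days | 17, past 12 weeks | not needed |
| 7, immunosuppressive, biological, antineoplastic, glucocorticoid | 3 months | none | 17, past 12 weeks | no |
| 8, live vaccine | 3 months | none | 15, past 12 weeks, any vaccine | no |
| 9, nuts or shellfish | 3 days | none | none | no |
| 11, travel | 6 months | yes, travel outside Canada since last donation | 14 and 35 | not needed |
| 5, incarceration | lifetime | none | 34, past 12 months and over 72 hours | partly (same serology) |

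**Count.** Of the five donation-timed exclusions, one (11) is covered by Appendix B, one (7) is covered for 1 of its 5 drug classes, and three (4, 8, 9) are not asked at all.

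**Would repeating Appendix C close the gap?** Two months is 2 × 52 / 12 ≈ 8.7 weeks. That is shorter than the 12-week look-back for vaccines and drugs and the 12-month look-back for tattoo and piercing. If Appendix C were completed at each rescreen, an event between two screens would fall inside the next look-back, and material still in quarantine could be withheld. This works for 4, 7 and 8. It does not work for 9, which neither form asks about. If only the laboratory tests are repeated, nothing in the document asks about any of the four again.

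**Item 34 against exclusion 5.** A donor jailed for a week two years ago, or for 48 hours last month, truthfully answers no to item 34. The criterion excludes both. Repeating the questionnaire would not cure this, because the mismatch lies in the wording of the question.

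**The case against.** The strongest reply is that Appendix B is only one layer. Appendix A has donors screened at baseline and at least every 2 months, and its next sentences count the questionnaire as part of screening. Exclusions 13 and 14 are counted back from screening, which suggests that history is retaken then. The text names laboratory tests as repeated; it does not say that nothing else is. This stands in part: a repeat of Appendix C is neither stated nor ruled out.

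A reader might therefore infer more than the document supports:

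- **That a newly excluded donor's stool necessarily reaches a patient.** This is certain only for the per-donation form. The rescreen and the quarantine may intervene.
- **That the questionnaire answers date from 2012.** The donors have been used since then, but Appendix C asks about COVID-19, so this version cannot have been completed that early. The date of last completion is not given.
- **That infection risk is uncontrolled.** Repeat serology addresses much of the blood-borne hazard behind tattoo, transfusion, and sexual or needle exposure. Exclusion 6 (transfusion from outside Canada) is partly captured by the Appendix B rows on travel, medical tourism and hospital care.
- **That incarceration belongs with the timed items.** It is a lifetime criterion, and the initial detailed history might find it even where item 34 does not.
- **That the number of collections per patient measures the gap.** One donor supplies each patient, so the count largely repeats the same donor's status.

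The donor consent form is not available for review, so any duty on donors to report changes cannot be judged. None of this supplies a stated check on a recent live vaccine, "systemic immunosuppressive or biological agents, systemic antineoplastic agents and exogenous glucocorticoids in the preceding 3 months prior to stool donation", or nut and shellfish intake.

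**Conclusion.** The point holds in a limited form. Appendix B omits exclusions 4, 8 and 9 and the non-antibiotic part of 7, although Appendix A ties all of them to donation. The protocol states no repeat of the questionnaire that would cover 4, 7 and 8, and no form covers 9. After allowing for serology and quarantine, the clearest remaining gaps are live vaccine, four of the five drug classes in exclusion 7, and allergen intake. Item 34 is a separate contradiction with exclusion 5.

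The conclusion rests on the forms as printed and on Appendix C not being routinely repeated, which the text leaves open. How often a donor would meet one of these exclusions between screens cannot be estimated from the document. No endpoint, sample size or analysis is affected. This is an alignment of forms with criteria, worth making because it is cheap and bears on recipient safety.

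**What to change.** 1. Add rows to the Appendix B checklist for the donation-timed items it omits, each with the Appendix A window: tattoo or piercing; immunosuppressive, biological, antineoplastic or glucocorticoid drugs; live vaccine; and nut or shellfish intake, for use where the recipient has the allergy.
2. State in Appendix A that Appendix C is completed again at each 2-monthly rescreen and reviewed before material leaves quarantine.
3. Reconcile Appendix C item 34 with exclusion 5, so that the form asks exactly what the criterion excludes.

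The cost is a revision of two forms, one added sentence, about a minute more per donation and an occasional rejected donation.

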Appendix B: Stool collection instruction for donors (to be filled out with each stool collection)

Stool collection for human biotherapy/ fecal microbiota transplantation

1. Do not take any medications (laxatives, anti-diarrheal drugs, mineral oil, bismuth, magnesium, or kaolin) for at least 3 days prior to and during the specimen collection. If you have been taking antibiotics in the last 90 days, you should not be collecting stool.
2. Make sure you have not had fever, vomiting, diarrhea or other symptoms of infection within the last 30 days. **Inform the investigator if you have any of these symptoms, as you should not donate stool. Please hand in this form with your stool collection with each donation.**

Day of FMT Procedure/donor Checklist		
Donor Name:	Yes	No
Do you feel well and healthy today?		
Have you had any fever, vomiting, diarrhea, cough, sore throat or other symptoms of infection within the last 30 days?		
If yes, specify:		
Antibiotics within past 90 days?		
Any medications (laxatives, anti-diarrheal drugs, mineral oil, bismuth, or magnesium, kaolin) in the past 3 days		
Since your last donation have you started working as a healthcare worker or worked in a long term care facility?		
Since your last donation have you been hospitalized or been treated in a long term care facility?		
Since your last donation, have you had medical treatment requiring frequent, regular attendance at outpatient medical or surgical clinics? If yes, please list dates and reason:		

Since your last donation, have you engaged in medical tourism i.e. travelled outside Canada for medical treatment?			
Since your last donation, have you had contact with anyone who has been diagnosed or suspected to have COVID-19?			
Since your last donation, have you travelled outside of Canada?			
Since your last donation, have you been diagnosed with COVID-19?			

3. Collect the specimen into the commode specimen collection system provided (Fisher 07544208) at home. This system fits under the toilette seat in center of rear of bowl. Do not mix with urine, paper or water. Once stool has been collected, snap on the lid provided to seal the container. Make sure you collect at least 100 g of stool, which is about the size of 4 Timbits donuts.
4. Place the container in the plastic bag supplied by the designate. Seal the bag tightly.
5. Mark date and time of collection and your initials on the lid.
6. Wash hands with soap and water when finished.
7. Maintain stool sample at 2°C to 8°C until specimen can be delivered to University of Alberta Hospital. Keep an ice pack in the bag with stool sample to keep it cold during delivery.
8. Please return specimen within 12 hours of collection and give to the hospital staff designate.

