Appendix C: Donor Questionnaire for human biotherapy/fecal microbiota transplantation

	Yes	No
Are You		
1. Feeling healthy and well today?		
2. Have you experienced a fever, cough, sore throat or any other sign of respiratory or other infectious illness in past 14 day?		
3. Currently taking an antibiotic?		
4. Currently taking any other medication for an infection?		
5. Currently taking any immunosuppressant medication by mouth or injection?		
6. Have you taken any antibiotics in the past 6 months?		
7. Have you had any fevers, vomiting, diarrhea or other symptoms of infection within the past 4 weeks?		
Do you have		
8. History of chronic diarrhea persisting > 10 days?		
9. History of blood in stool not related to hemorrhoid?		
10. History of change in bowel habit, alternating from constipation to diarrhea?		
11. Any type of active cancer that is not cured?		
12. Any active autoimmune diseases?		
In the past 12 weeks have you		
13. Have you been in contact with anyone who has been diagnosed or suspected to have COVID-19?		
14. Have you travelled outside Canada?		
15. Had any vaccinations? If yes, please indicate which one(s)		
16. Had contact with someone who had a smallpox vaccination?		
17. taken antibiotics, systemic immunosuppressive or biological agents, systemic antineoplastic agents and exogenous glucocorticoids? If you have, you should not be a stool donor.		
In the past 16 weeks have you		
18. Lived with a person who has hepatitis A?		
19. If yes, have you received vaccine against hepatitis A?		
In the past 12 months have you		

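### The donor symptom question looks back 30 days but stool is banked for at least 5 weeks, so an undiagnosed illness soon after a donation can go unasked before release

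*Protocol*

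**What the plan says.** Four parts of the Protocol bear on this.

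- **Collection form (Appendix B).** It is headed "Stool collection instruction for donors (to be filled out with each stool collection". Its symptom item reads "Have you had any fever, vomiting, diarrhea, cough, sore throat or other symptoms of infection within the last 30 days". Seven of the other ten questions on the form instead cover the whole time since the previous donation, for example "Since your last donation, have you been diagnosed with COVID-19".
- **Quarantine (Appendix A).** Stool is held until the donor has passed two consecutive screens. In addition, "to minimize COVID-19 transmission risk, the quarantine period is at least 5 weeks as per Health Canada directions".
- **Re-screening (Appendix A).** Of the donors it says: "They are screened at baseline and then every 2 months at a minimum for the duration of the trial". Only the blood work and stool testing are expressly said to be repeated. The listed tests include hepatitis A IgM in blood. They include no SARS-CoV-2 test (the nasal swab is for MRSA) and no viral test on stool.
- **Other symptom look-backs.** Donor exclusion 15 in Appendix A reads "History of a fever, cough, sore throat or any other signs of respiratory or other infectious illness in the past 14 days". Item 2 of the Appendix C questionnaire also uses 14 days. Item 7 reads "Have you had any fevers, vomiting, diarrhea or other symptoms of infection within the past 4 weeks".

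No symptom question at release is stated, no maximum interval between donations is set, and nothing links a later report of illness to units already in store. Section 3.4 has the other sites use an identical donor-screening protocol, so the point applies to all three.

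**The concern.** Holding stool after donation helps in two ways. It allows later tests, and it gives time to learn whether the donor fell ill soon afterwards, which would suggest that the stool was given during incubation. The second benefit needs a question that reaches back to the donation date. The longest symptom look-back here is 30 days and the shortest quarantine is 35 days, so the question need not reach that far.

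At stake is the release, under the plan as written, of stool given while the donor was incubating an infection. The recipients have severe or fulminant disease, and infection related to FMT is one of the serious events that section 3.72 sets out to count.

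**Working it through.** The Protocol gives no figure to reproduce, so the check is interval arithmetic.

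**Inputs.** Look-backs: 30 days (Appendix B), 4 weeks = 28 days (Appendix C, item 7), 14 days (exclusion 15; Appendix C, item 2). Minimum quarantine: 5 weeks = 35 days (Appendix A). Re-screen interval: at least every 2 months, taken as 60 days.

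**Formula.** If a question with look-back L is put T days after a donation, the days after donation that it does not cover are max(0, T − L).

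| Question put on day | 30-day item | 28-day item | 14-day items |
|---|---|---|---|
| 35 | 35 − 30 = 5 | 35 − 28 = 7 | 35 − 14 = 21 |
| 60 | 60 − 30 = 30 | 60 − 28 = 32 | 60 − 14 = 46 |

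The 30-day column is the one that counts, because that item is expressly repeated at every collection. The other two columns apply only if the history and questionnaire are repeated at re-screening, which the text does not say.

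**Example.** A donor gives stool on day 0 and is ill on days 3 to 10. A 30-day question put on day 35 reaches back to day 5, and on day 40 to day 10, so either would pick the illness up. On day 45 it reaches back only to day 15, and the donor can truthfully answer no.

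**Can intervals exceed 30 days?** From section 3.5, one cycle plus the final enema uses 720 + 360 + 180 + 180 = 1,440 cc. Four cycles plus the final enema use 4 × 1,260 + 180 = 5,220 cc. At about 360 cc per donation (section 3.41) that is 4 to 14.5 donations per patient. There are five Edmonton donors (section 3.4), and recruitment is 30 patients over 2 years across all sites (section 3.2), taken as 730.5 days. The split by site is not given, so assume that Edmonton supplies 10 to 30 patients:

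- Longest mean interval: 10 × 4 = 40 donations, 40/5 = 8 per donor, 730.5/8 = about 91 days.
- Shortest mean interval: 30 × 14.5 = 435 donations, 435/5 = 87 per donor, 730.5/87 = about 8 days.

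These are means for trial demand alone. Collections may cluster around a patient, and Appendix A shows that the donors also serve other patients. Intervals over 30 days are possible, but the Protocol does not settle how common they are.

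**What else would catch the illness?** When the form is next completed, it asks about COVID-19 diagnosis, contact with a diagnosed or suspected case, and hospital stay since the last donation, and about antibiotics in the past 90 days. The screens would catch an infection on the test list that is still detectable. What remains is undiagnosed illness, without antibiotics, hospital stay or known COVID-19 contact, from a pathogen that is not listed or has cleared.

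**The case against.** The strongest reply is that the Appendix B form decides whether today's stool may be given, and 30 days is ample for that. Clearing earlier stool is a release step, which may be described in the manufacturing protocol or the Health Canada directions that the Protocol mentions but does not reproduce. Donors who give often are asked often. The form also tells donors to inform the investigator of symptoms.

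Part of this stands. A donor asked again within 30 days of the illness would disclose it, and release practice outside the Protocol cannot be ruled out. But the duty to inform is tied to not donating, not to recalling stored stool. The Protocol itself sets out quarantine and release conditions, and a symptom question is not among them.

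Some stronger inferences are tempting, and the documents do not support them:

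- *The quarantine gathers no symptom history for the days after donation.* It does when the donor is asked in time, as the question on day 35 or 40 shows.
- *The questions are the only check on enteric viruses.* Hepatitis A IgM is tested in blood. What is missing is any viral test on stool.
- *Only a diagnosed COVID-19 case is caught.* Contact with a diagnosed or suspected case is asked too.
- *The three look-backs contradict each other.* They serve initial eligibility, the questionnaire and each collection, and the longest applies at each donation.

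**Conclusion.** The point holds as a possibility that the written plan leaves open. At least 5 days after donation are uncovered if the symptom question is next put on day 35, and about 30 days if it is put on day 60. This arises only if the donor is not asked again within 30 days of the illness, and only for the residual kind of illness described above.

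It rests on two assumptions: that no unseen procedure adds a symptom question at release, and that 2 months means about 60 days.

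No probability can be attached. The Protocol gives neither an illness rate nor a donation schedule. Even an assumed illness rate would give the chance that an illness starts after a donation, not the chance that infectious stool is released. A reader might also infer that the FMT-related infection outcome is compromised. It is not, because a proven case would still be counted under section 3.72. The issue is recipient safety, and the change is worth making because it is cheap.

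**What to change.** - In Appendix B, word the symptom item 'since your last donation or within the last 30 days, whichever is longer', and record the onset date. This matches the neighbouring items and leaves 0 uncovered days whenever the form is completed.
- Put the same question to the donor before a quarantined unit is released, so that it covers the whole period since that donation. This also deals with a donor who has not given stool again in the meantime.
- Reconcile the look-back, quarantine and release passages in Appendices A, B and C, so that a positive answer triggers investigator review of units still in quarantine.

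The cost is form and SOP wording and one question per release. The downside is that a stored unit is occasionally held or discarded.
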